A Fisher's exact test will be used to test the 48 hour seizure cessation rate between the two treatment groups. As a secondary reanalysis, multivariate logistic regression (if there are sufficient number of events), will be performed to study the association between cessation rates and treatment. Any baseline covariates (including stratification factors) that are simultaneously unbalanced between treatment groups at baseline (univariate $p < 0.10$) and associated with the outcome (univariate $p < 0.15$) will be included in the multivariable model as observed confounders. A similar approach will be utilized to analyze the 1-hour seizure cessation rates.

Power Analysis for Aim 1: Power calculations were based on a 2-sided chi-square test for detecting a difference between two proportions, assuming a Type 1 error of 0.05. With a sample size of 60 LEV subjects and 40 PB subject and assuming a seizure cessation rate of 50% in the control arm, we have 80% power to detect a seizure cessation rate as low as 22% (an absolute difference in seizure outcome rates of 28% or greater) in the LEV group.

Analysis Plan for Aim 2: Dose escalation analysis

The percentage of neonates whose seizures stop following 60mg/kg LEV, having not responded to 40mg/kg LEV will be calculated with the corresponding 95% confidence interval.

Analysis Plan for Aim 3: Pharmacokinetic analysis

The actual individual concentration data, collection times and dosing histories will be used to create graphs of plasma LEV concentration vs. time for each infant. Median plasma drug concentration vs. time curves will also be generated. Summary statistics (i.e., n, mean, standard deviation, median, minimum, maximum, and coefficient of variation) will be calculated for plasma concentrations for each time point and each dose level. LEV population pharmacokinetic parameters will be determined using the computer program NONMEM (ver. 6 or later). The data will be nested with existing raw infant LEV pharmacokinetic data generated in the preliminary LEV study. Assuming linear pharmacokinetics as suggested by our current pharmacokinetic data, studying 12 subjects at each dosage level will result in 90% confidence intervals for the pharmacokinetic parameters (CL, V and $t_{1/2}$) of +/- 15%. The 90% confidence intervals for the exposure parameters (C_{max} , AUC) will be approximately +/- 20%. The pharmacokinetics will be modeled recognizing the two stages of a nonlinear hierarchical model development. The first stage introduces the structural model (e.g. one compartment open model), the population parameters, individual effects and the within-patient variation. The second portion of the model development recognizes that variation between patients in the pharmacokinetic parameters exists and will attempt to determine covariates that may identify different pharmacokinetic subpopulations. A one-compartment model with first order elimination will be utilized. Alternative structural models will be explored if indicated by the data. The impact of clinical factors and demographic factors (including weight, sex, age, race, serum creatinine, hypothermia and dosing regimen) will be assessed as fixed effects in the model. Nested models will be compared graphically and with a likelihood ratio test.

Analysis Plan for Aim 4: Safety analysis

A Fisher's exact test will be used to compare rates of adverse events, serious adverse events and study discontinuation rates between the LEV and control groups.

Analysis Plan for Aim 5 A: Feasibility of remote continuous EEG monitoring system

Feasibility will be measured by accuracy and speed of notification of electrographic seizures. We will report the standard metrics of sensitivity and specificity. If Corticare reports a seizure rejected by the study investigator, this will be recorded as a false positive. Conversely seizures recorded by the neurophysiologist but missed by Corticare will be false negatives, and we will determine the rate of false positives and false negative seizure reports by Corticare technologists. We will calculate the specificity and sensitivity of Corticare seizure reporting. For speed of reporting, we will measure the time lapse between the occurrence of seizure and site study investigator notification and the lapse between occurrence of seizure and study drug administration. Descriptive report of technical difficulties experienced with the remote centralized EEG review system will be made.

Analysis plan for Aim 5 B. Analysis of performance of the automated seizure detection algorithm

In addition to standard visual EEG review by the study's electroencephalographers, the early detection of seizures will be assisted by automated seizure detection notifications generated by the computerized algorithm. These notifications, and images of their associated EEG tracing and graphical trends, can be automatically broadcast via email to specifically designated study personnel for verification of the nature of the detected event. The performance of the seizure detection algorithm will be assessed by comparing its output to the final EEG markings of two neonatal electroencephalographers. The following seizure detection algorithm performance parameters will be calculated: overall seizure detection sensitivity, false positive rate, and seizure-affected patient detection rate (the percentage of patients with seizures in whom at least one seizure is correctly identified).

9. HUMAN SUBJECTS:

The trial will be a Phase II trial to test the efficacy, pharmacokinetic and safety of intravenous Levetiracetam (LEV) as first line treatment for neonatal seizures with greater than minimal risk.

Human Subjects Involvement and Characteristics

Subject characteristics: This trial will be conducted in term-age newborns with seizures who are admitted to the neonatal intensive care units (NICUs) at one of five participating hospitals, namely Rady Children's Hospital University of California, San Diego, UCSD Medical Center, Sharp Mary Birch Hospital San Diego, Children's Hospital and Research Center Oakland, and Auckland Hospital. The subjects will have a corrected gestational age at birth of 36-44 weeks and a postnatal age of < 14 days. Subjects are expected to be critically ill newborns, reflecting the underlying etiology of the seizures as well as the physiologic effects of seizures per se. Approximately 50% of neonatal seizures are caused by hypoxic ischemic encephalopathy, (HIE). These infants have sustained global hypoxic ischemic injury with consequent renal, hepatic, gastrointestinal, respiratory and cardiac sequelae. Other common etiologies of neonatal seizures include intracranial hemorrhage, infection and developmental defects, which may also be associated with impaired function of other organs. Therefore seizures are frequently associated with high mortality and morbidity. 20-30% of infants with neonatal seizures die, 20-30% develop epilepsy outside the neonatal period, and 20-40% develop cerebral palsy and/or mental retardation⁶

Rational for enrolling newborns as subjects: There are several important factors contributing to the rationale for involving term newborns in this research. The drug to be studied has been extensively studied in adults and older children and shown to be safe and effective. It cannot be assumed however that this will mean that the drug is safe or effective in neonates without study in this population. The neonatal response to AED's is fundamentally different to that of the mature brain. Agents that have good efficacy and safety in the mature brain, (Phenytoin and Phenobarbital) are much less effective and have increased toxicity in the immature brain.

There is an urgent need for safe and effective treatments in this neonatal population. Currently used treatments are poorly effective and have significant side effects, none are FDA approved. The incidence of seizures is higher in newborns (2-3.5 per 1000 live births) than at any later age. Neonatal seizures are often

refractory to treatment and lead to frequent and serious long-term consequences in survivors, such as significant cognitive and motor disabilities and later epilepsy.

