Subjects randomised to receive LEV will, at the onset of electrographically confirmed seizure activity, receive an intravenous loading dose of LEV of 40mg/kg given over 15 minutes. If electrographic seizures are confirmed to persist or recur more than 15 minutes after the first infusion is complete, a further 20mg/kg load of LEV will be administered IV over 15 minutes. Maintenance LEV at 10 mg/kg/dose will be given IV q8 hours and continued for at least 5 days. If seizures persist or recur more than 15 minutes after the second LEV infusion is complete, a PB loading dose of 20 mg/kg will be administered IV over 15 minutes. If seizures persist or recur more than 15 minutes after the first loading dose of PB is complete, a second 20mg/kg load will be administered IV over 15 minutes. This will result in PB being started within 1 hour of the onset of seizures if and when loading with LEV is ineffective. Patients given any PB loading doses will be started on maintenance PB with 1.5 mg/kg/dose given IV q8 hours and continued at least until the end of the study

Figure 2 details the study flow.

Subjects randomized to the control group will, at the onset of electrographically confirmed seizure activity, receive an intravenous loading dose of PB of 20 mg/kg given over 15 minutes. If electrographic seizures are confirmed to persist or recur more than 15 minutes after the first infusion is complete, a further 20mg/kg load of PB will be administered IV over 15 minutes. Maintenance PB at 1.5 mg/kg/dose will be given IV q8 hours and continued for at least 5 days. If seizures persist or recur more than 15 minutes following the second PB infusion, a 40 mg/kg load of LEV will be administered IV over 15 minutes. If seizures persist or recur more than 15 minutes after the first loading dose of LEV is complete, a second 20mg/kg load of LEV will be administered IV over 15 minutes. Patients given an LEV loading doses will be started on maintenance LEV with 10 mg/kg/dose given IV q8 hours and continued at least until the end of the study.

If electrographic seizures are still apparent following treatment with both LEV and PB, or if they recur during the 5 days during which the study protocol is active, the patient will be considered to have failed the experimental treatment regime and institutional specific standard seizure management will dictate the ongoing

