EEG data monitoring and automated seizure detection: Gold standard 9 channel neonatal montage continuous video-EEG data will be collected for 24 to 48 hours after study drug administration with the length of monitoring time determined by the Principal Investigator for each site. There may be infants who, after 24 hours of remaining seizure-free, are appropriate for discontinuation of monitoring which also may enable them to be safely discharged home. Babies undergoing hypothermia for hypoxic ischemic encephalopathy will have EEG monitoring data captured for 24 hours post start of rewarming as this is a high risk time for seizures. Each site will use available video EEG equipment with Persyst software installed. A research dedicated Cadwell video EEG system is requested under this grant for each site. Following recruitment to monitoring, each site will have their study investigator monitoring the EEG in real time, per the study algorithm. Corticare technicians will provide continuous EEG monitoring by remote access to the acquisition station. If Corticare or the real time onsite observer detects seizure activity the site investigator or local encephalographer will immediately be contacted to review the tracing. Neonatal EEG data obtained from conventional digital EEG machines based at the study sites will be monitored in near- real time using Persyst Insight software running

on the acquisition stations via the site's local area network or remotely via secure Internet access utilizing Citrix server, Microsoft Remote Desktop, or similar institutional remote access capabilities. The EEG data will be continuously analyzed in near- real time using Persyst MagicMarker in order to produce and display EEG data trend graphs. The graphical EEG trends will include Rhythmic Run Detection and Display, amplitude integrated EEG, FFT spectrograms, asymmetry spectrograms, and other trends useful in the rapid recognition of seizures. Following completion of the local study on each subject the full video EEG (totalling 5 Gigabytes of data/ 24 hours) will be archived on the UCSD server for analysis by the encephalographers. Data transfer will be achieved where possible by encrypted internet connections. Alternatively the studies will be mailed on memory sticks or DVDs. Archived video continuous EEG data will be available for trend analysis and seizure detection comparison with the duplicate formal encephalographers reading of the 48 hours of tracing.

Add on Study:

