Data that will be collected specifically for the purposes of this trial will include clinical data regarding the subjects' medical history and hospital course including clinical characteristics such as weight, medications administered, blood pressure measurements, and fluid input/output. Most clinical data will be obtained from the subjects' medical records, but there may be some data obtained by interviewing the parent(s).

Much of the laboratory data that will be recorded in the database will be laboratory data obtained in newborns as part of standard clinical care of newborns with seizures, such as serum blood gas measurements, serum electrolytes, levels of AEDs administered and liver function tests. Some laboratory tests such as albumin and serum bicarbonate may not be collected at both time points for standard care for some subjects and thus will be obtained for purposes of the trial. Serum LEV levels will be collected only for purposes of this trial.

EEG data will be read and used for clinical purposes at each site with the assistance of the remote centralized continuous monitoring system. For the purposes of the study itself EEG data collected at each site will be de-identified before analysis by the study neurophysiologists who will be blinded to the subjects' group assignment or demographic information.

Study staff at each site will have access to individually identifiable information about newborns enrolled at that site. Data will be collected by each site's study investigators and the research coordinator and recorded onto case report forms (CRFs) by the research coordinator, and data from the CRFs will subsequently be entered into the database by the research coordinator. The CRFs and the electronic database will only have de-identified information to preserve confidentiality of patients' protected health information. Files that link the study identification number for each subject to the subject's personal information (such as name, medical

record number, parents' names) will be kept at each site and accessible only by the site PI and research coordinator.

10. RECRUITMENT AND SCREENING:

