- B. Infants admitted to NICU with pathologies other than HIE that also place the infant of high risk to develop seizures.
- C. Infants with seizures as first indication of illness, transferred to the NICU for treatment. Initially etiology may not be clear but may include infection, stroke, hemorrhage, brain malformation and idiopathic seizures.

Partial HIPAA waiver will need to be granted for the recruitment procedure, specifically the waiver of consent for the transfer from the clinical team to the study team of clinical information needed to determine patient eligibility for the study.

In groups A + B it will be possible to prospectively obtain consent for participation in the trial at the time when the infant is admitted to the unit. Neonatal staff (Admitting neonatal fellow or resident) will identify eligible subjects in group A or B briefly discuss the study with patients' families and obtain permission to contact study staff. Study staff will screen the patient for inclusion and exclusion criteria as listed above and obtain consent from parents for participation in the study in the event that seizures should occur

Group C:

Frequently seizures are the first indication that a neonate is unwell. These occur in the regular postnatal nursery. Once the infant is transferred to the NICU and stabilized cardiovascularly, and if seizures are ongoing and hypoglycemia and hypocalcemia have been excluded as cause for the seizure, a continuous EEG monitor will be placed, (this is not yet standard of care in the majority of NICU's in the United States but is an option available in many centers).

While the EEG leads are being placed intensive efforts will be made by neonatal and study staff at this stage to obtain parental consent for participation in the study. If consent can be obtained the patient will be enrolled in study and a randomized to a treatment arm during the EEG set up. If electrographic seizures are confirmed, IV treatment with study drug according to the protocol will commence.

11. INFORMED CONSENT:

1. The admitting resident or fellow who identifies seizures or high risk of seizures developing in the future will request the parents' permission for the study staff to approach them to discuss their possible participation.

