## 6 Statistical Methods

### 6.1 Analysis Populations

- Intent-To-Treat [ITT] population: All randomized participants.
- Per-Protocol (PP) population: Excluding babies not following the protocol.
- Subset Populations: Hypoxic-Ischemic Encephalopathy (HIE); Cooled/not cooled

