## 7.3 Analysis of Primary and Key Secondary Outcomes

### Primary Hypothesis

Hypothesis: Treatment with LEV improves the rate of seizure termination at 24 hours in neonates compared with standard PB treatment.

Analysis Plan: A Fisher's exact test will be used to test the 24 hours seizure termination rate between the two treatment groups. As a secondary analysis, multivariate logistic regression (if there are sufficient number of events), will be performed to study the association between termination rates and treatment. Pre-specified covariates, including seizure etiology (HIE vs Other)

CONFIDENTIALITY STATEMENT: This report from the USC Alzheimer's Therapeutic Research Institute (ATRI) is for the sole use of the intended recipient(s) and contains confidential and privileged information. Any unauthorized review, use, disclosure, copying or distribution is strictly prohibited.

and hypothermia treatment (yes, no), will be included in the multivariable model as observed confounders.

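### Study drug starts on a local real-time EEG call, and no visible rule ties the analysed set to a pre-dose seizure that the blinded EEG readers confirm

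*Protocol*

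**What the plan says.** **Trigger.** Protocol section 8 (Study Design Summary) starts treatment in the LEV arm with infants who, "at the onset of electrographically confirmed seizure activity, receive an intravenous loading dose of LEV"; the control arm starts PB on the same event. The visible text gives no minimum number or duration of seizures. For infants who present acutely, Protocol section 10 allows randomisation during EEG set-up and then states: "If electrographic seizures are confirmed, IV treatment with study drug according to the protocol will commence".

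**Who makes the call.** In the section 8 text on EEG monitoring, a site investigator watches the EEG and remote technicians watch in parallel. If either detects a seizure, "the site investigator or local encephalographer will immediately be contacted to review the tracing". This is an EEG review at the site in real time.

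**Who reads the EEG for the study.** After the infant's local study ends, the full video EEG "will be archived on the UCSD server for analysis by the encephalographers". Protocol section 9 adds that, for study purposes, the EEG "will be de-identified before analysis by the study neurophysiologists who will be blinded" to group assignment.

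**What is analysed.** SAP 3.6 counts success as seizures stopped for 24 hours without a second anticonvulsant, and SAP 4.1 names no assessor. SAP 6.1 reads "Intent-To-Treat [ITT] population: All randomized participants"; its per-protocol set removes only infants who did not follow the protocol. SAP 7.3 states: "A Fisher's exact test will be used to test the 24 hours seizure termination rate between the two treatment groups".

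**The concern.** Entry to dosing and the outcome both turn on whether a seizure is present, but different readers may judge the two at different times. Take an infant dosed on a local call that the blinded readers would mark as artefact or non-seizure. With no later seizure and no second drug, this infant meets the 24-hour outcome on either treatment, although there was nothing to terminate. The per-protocol set does not clearly remove the infant, because dosing on a good-faith local call follows the protocol.

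Two things are at stake. The arm difference is diluted, which costs power. The response rates may also be too high, and Protocol section 8 (rationale for a phase II study, and the plan for statistical analysis) intends to use this trial for the phase III decision and sample size.

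**Working it through.** **Inputs.** SAP 3.4 gives 60 LEV and 40 PB infants, 50% response on PB, 22% detectable on LEV, two-sided alpha 0.05 and 80% power. SAP 7.3 gives Fisher's exact test. The share f of dosed infants whose qualifying seizure the blinded readers do not uphold is not in the documents. I assume 2% to 20%.

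**The plan's own figure.** SAP 3.4 names a chi-square test. The uncorrected normal approximation has pooled rate (40×0.50 + 60×0.22)/100 = 0.332. Its null standard error is √(0.332×0.668×(1/40 + 1/60)) = 0.0961, and its alternative standard error is √(0.25/40 + 0.1716/60) = 0.0954. Then z = (0.28 − 1.96×0.0961)/0.0954 = 0.96, which gives 83.1% power. For Fisher's test, power is the sum over all outcome pairs (a, b) of Bin(a; 40, p₁)·Bin(b; 60, p₂), counting pairs with p ≤ 0.05. This gives 79.6%, which matches the stated 80% and is the reference below.

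**Dilution with no rescue.** If every unconfirmed infant counts as a responder, the observed rate in each arm is f + (1 − f)p, and the 28-point difference becomes 28(1 − f). For example, at f = 10%, PB is 0.10 + 0.90×0.50 = 55.0% and LEV is 0.10 + 0.90×0.22 = 29.8%, a difference of 25.2 points. SAP 7.3 hypothesises that LEV is better, so the table also shows the mirror case of 78% on LEV. The confirmed set keeps the undiluted rates at the smaller n.

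| f | PB / LEV worse | Power | PB / LEV better | Power | Confirmed set (LEV/PB) | Power |
|---|---|---|---|---|---|---|
| 0 | 50.0% / 22.0% | 79.6% | 50.0% / 78.0% | 79.6% | 60/40 | 79.6% |
| 2% | 51.0% / 23.6% | 76.8% | 51.0% / 78.4% | 78.5% | 59/39 | 80.0% |
| 5% | 52.5% / 25.9% | 72.6% | 52.5% / 79.1% | 76.7% | 57/38 | 79.0% |
| 10% | 55.0% / 29.8% | 66.3% | 55.0% / 80.2% | 73.5% | 54/36 | 75.9% |
| 20% | 60.0% / 37.6% | 55.2% | 60.0% / 82.4% | 66.3% | 48/32 | 69.8% |

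The 80.0% at f = 2% lies above 79.6% only because the exact test moves in steps. The confirmed-set power is the same in both directions.

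**Half rescued, f = 10%.** If half of the unconfirmed infants go on to a second drug after a further local call, the observed rate is 0.05 + 0.90p. PB stays at 50.0%. LEV becomes 24.8% (from 22%) or 75.2% (from 78%). Unrestricted power is 68.7% in both directions, against 75.9% in the confirmed set.

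**The case against.** **False calls appear to be caught before dosing.** Protocol section 8 (Aim 5A analysis) counts remote reports that the study investigator rejects. Protocol section 10 describes myoclonic jerks correctly identified on EEG, so that some infants were spared drug. Both are filters upstream of treatment. Neither shows blinded readers overturning a call that the site investigator or local encephalographer has confirmed. A reader might infer that false calls are known to reach dosing at some material rate; the documents do not support that, and f may be small. This stands.

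**No rescue is the extreme case for inflation.** The local reviewers who over-call once also make the later calls, and a second drug means failure. With half rescued, the PB rate is not inflated at all. This stands for the rates. The power loss remains.

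**The gain is modest in the hypothesised direction.** With LEV better and no rescue, the confirmed set gains about 1.5, 2.3, 2.4 and 3.5 points at f = 2%, 5%, 10% and 20%. Nor does restriction bring back 79.6% at the larger f, because infants are lost. The model also treats 50% as the rate in truly seizing infants, which SAP 3.4 does not say. All of this stands.

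**The two-reader account is partly inferred.** SAP 4.1 names no assessor; that the blinded readers score the outcome rests on Protocol section 9. The duplicate formal reading in section 8 covers 48 hours of tracing and is tied to the detection comparison, and the note closing SAP 3.2 takes Aims 5A and 5B out of the primary analysis. A formal pre-dose reading is therefore not clearly planned. The flow figures could not be read, so a rule shown only there cannot be excluded.

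**A confirmed set excludes infants after randomisation.** This departs from the all-randomised wording of the protocol and SAP. Readers who see the whole record may also mark an equivocal pre-dose event more readily when seizures follow. Both points stand and shape the fix.

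**Conclusion.** The gap is real and worth closing, but its size is unknown. The visible text on eligibility, outcomes, populations and analysis does not say what happens when the blinded readers do not find the qualifying seizure. The dilution works toward no difference. A reader might infer bias in favour of one drug, but with similar false-call rates in both arms the documents give no ground for that.

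The figures rest on an assumed f that is equal in both arms. Over 2% to 20%, the confirmed set has more power in every case computed, from about 1.5 points (LEV better, f = 2%) to 14.6 points (LEV worse, f = 20%: 69.8 − 55.2). Inflation of the response rates is greatest with no rescue and can vanish with partial rescue. The case for change rests as much on interpretable phase III planning rates, and on settling the rule before unblinding, as on power.

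**What to change.** In SAP 6.1 and 7.3, before unblinding:

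- Define a modified ITT efficacy set: randomised and dosed infants with at least one electrographic seizure before the first study-drug infusion, as marked by the blinded neurophysiologists.
- Have them read the pre-dose segment without knowledge of arm and without the post-dose EEG, so that the response cannot influence the confirmation.
- State a rule for reader disagreement, for example keeping the infant if either reader marks a seizure.
- Use this set for the 24-, 48- and 1-hour outcomes.
- Report the same outcomes in all randomised and dosed infants alongside, and give the number unconfirmed in each arm. The comparison set is dosed infants because randomisation can precede any seizure, and the SAP defines no outcome for infants who are never dosed.

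The cost is SAP wording, a short extra read of EEG that should already be archived, and a few fewer infants in the efficacy set. The exclusion follows randomisation and differs from the stated all-randomised principle, which is why the unrestricted result should stand beside it.

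### Aim 5A scores Corticare's false positives and its misses against different readers, and promises a specificity without a unit of negatives

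*Protocol*

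**What the plan says.** Protocol section 8, Analysis Plan for Aim 5 A, judges the feasibility of remote monitoring by the accuracy and speed of seizure notification. The accuracy part rests on three statements:

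- Over-calls: "If Corticare reports a seizure rejected by the study investigator, this will be recorded as a false positive".
- Misses: "seizures recorded by the neurophysiologist but missed by Corticare will be false negatives".
- Summary measures: "We will calculate the specificity and sensitivity of Corticare seizure reporting".

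The same paragraph promises rates of false positive and false negative reports, without a denominator. It defines neither a true positive nor a true negative, and it does not say whether the unit is an epoch, an hour or an infant.

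The readers' roles are described elsewhere. Under EEG data monitoring and automated seizure detection (section 8), "each site will have their study investigator monitoring the EEG in real time", and once an alert is raised "the site investigator or local encephalographer will immediately be contacted to review the tracing". The same part plans to archive the full video EEG for a duplicate formal reading by encephalographers. Section 9 says that the EEG is "de-identified before analysis by the study neurophysiologists who will be blinded". That blinding is to group assignment and demographic information; Corticare's alerts are not mentioned.

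Aim 5B, analysed in the next paragraph, uses one reference for the detection algorithm: the final markings of two electroencephalographers. Its analysis plan lists sensitivity, a false positive rate and a patient-level detection rate.

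SAP section 3.2 restates Aims 5A and 5B. A note in capitals after the aims then says that neither is part of the primary analysis, because monitoring changed during the study. SAP section 7 gives no method for either.

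**The concern.** A table of test results against truth needs one definition of truth. Here the study investigator decides which reports were wrong, and the neurophysiologist decides which seizures were missed. The investigator is prompted by the very alert that is being scored. A report that the investigator rejects in real time, but that the formal reading later marks as a seizure, counts as a false positive although that reading supports it. A report that the investigator accepts and the formal reading does not mark escapes being counted as false.

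Specificity needs a count of negatives, and continuous EEG has none until someone divides the record into units. With the unit left open, the choice can be made after the data are seen.

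Aim 5A is meant to show whether remote monitoring can serve later neonatal seizure trials, so its accuracy figures are likely to be reused. On the present rule the false-positive figure and any specificity would partly reflect the investigators' errors. They would not sit on the same reference as the misses, nor as the Aim 5B results.

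**Working it through.** The documents give no target, sample size or expected value for Corticare's accuracy, so there is no planned figure to reproduce. The check applies the stated rule to assumed inputs.

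**1. False positives under the mixed rule.** Assume 100 seizures marked on the formal reading. Corticare reports 80 of them, misses 20, and makes 20 further reports that the formal reading does not mark. Let r be the share of the 80 that the investigator wrongly rejects, and a the share of the 20 that the investigator wrongly accepts. Then

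false positives = 80r + 20(1 − a).

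If a true positive is taken to mean an investigator-accepted report, there are 80(1 − r) + 20a of them, and sensitivity is that number divided by itself plus the 20 misses.

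| r | a | False positives | Accepted reports | Sensitivity on accepted reports |
|---|---|---|---|---|
| 0% | 0% | 20 | 80 | 80/100 = 80.0% |
| 10% | 25% | 8 + 15 = 23 | 72 + 5 = 77 | 77/97 = 79.4% |
| 25% | 25% | 20 + 15 = 35 | 60 + 5 = 65 | 65/85 = 76.5% |
| 10% | 50% | 8 + 10 = 18 | 72 + 10 = 82 | 82/102 = 80.4% |

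The first row is the single-reference result. The others show that the false-positive count can move up or down. Nothing about Corticare or the formal reading differs between rows; only the investigator's errors do. In the last three rows the sensitivity denominator is 97, 85 or 102, although the formal reading marked 100 seizures.

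**2. Sensitivity on one reference.** False positives do not enter sensitivity. If a true positive is a neurophysiologist-recorded seizure that Corticare reported, sensitivity is 80/(80 + 20) = 80.0% in every row.

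**3. Specificity by choice of unit.** Assume that false alarms occur at a constant rate λ per hour in seizure-free time, as a Poisson process. Specificity for units of length h hours is then the chance of no false alarm in a unit, exp(−λh). Protocol section 7 gives about one false detection per 11 hours for the detection algorithm. That figure is not Corticare's; it is borrowed as an assumption, with a range around it. The 24 and 48 hour columns correspond to the planned monitoring time after study drug.

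| Assumed rate | 10 seconds | 1 minute | 1 hour | 24-hour record | 48-hour record |
|---|---|---|---|---|---|
| 1 per 24 h | 99.99% | 99.93% | 95.9% | 36.8% | 13.5% |
| 1 per 11 h | 99.97% | 99.85% | 91.3% | 11.3% | 1.3% |
| 1 per 4 h | 99.93% | 99.58% | 77.9% | 0.2% | below 0.01% |

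For example, at 1 per 11 h the one-hour figure is exp(−1/11) = 0.913 and the 48-hour figure is exp(−48/11) = 0.013. Each row describes the same monitoring performance.

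**The case against.** A reader might infer that Aim 5A's sensitivity is invalid. The text does not support that. Misses are tied to the neurophysiologist, and a coherent sensitivity on that reference can be read from the plan. It becomes mixed only if true positives are investigator-accepted reports, which the plan neither says nor excludes.

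A reader might also infer that specificity can never be computed. That goes too far as well. Negatives exist per epoch, per hour or per infant, and specificity follows once a unit is chosen. Replacing it with a false-positive rate is one reasonable option, not the only valid one. Aim 5B is not a perfect model either: its aim statement also speaks of specificity, and only its analysis plan uses a false positive rate.

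The identity of the readers is partly inferred. The Aim 5A paragraph does not tie its neurophysiologist to the archived formal reading, and section 8 also allows a local encephalographer to review alerts in real time. Section 9 supports reading them as separate people. If the sponsor meant one reader, the paragraph has to say so, and the wording needs correcting either way.

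Rejection by the responsible investigator is a legitimate measure of operational false alarms. That stands, and is a reason to keep it under its own name.

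Finally, Aim 5A has no hypothesis test or decision threshold, the SAP takes it out of the primary analysis, and Protocol section 11 already refers to closed recruitment. The monitoring changes may have overtaken the rule. This limits the severity. It does not dispose of the point: SAP section 3.2 keeps the aim, SAP section 5.2 refers to planned analyses in the research plan as well as the SAP, and no replacement method is given.

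**Conclusion.** The point holds, at low severity. The stated rule takes false positives from one reader and misses from another, so it can count as false a report that the formal reading supports. In the illustration it gives 23, 35 or 18 false positives in place of 20. The arithmetic is exact, but the investigator error rates are assumptions with no source in the documents.

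Specificity is undetermined as written. At the borrowed rate of one false alarm per 11 hours it runs from 99.97% to 1.3% depending only on the unit. Sensitivity is sound on one definition of true positive, and that definition is missing; on the other definition it moved by at most 3.5 points (80.0% to 76.5%) in the settings shown.

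It would be wrong to infer that the trial's efficacy or safety results are affected. The point concerns only a separate report of Aim 5A.

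**What to change.** Before any Aim 5A result is reported, amend the analysis wording as follows:

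- Score every Corticare report and every miss against the planned formal reading of the archived EEG, as Aim 5B does.
- Define a true positive as a seizure marked on that reading and reported by Corticare, and a false positive as a report that the reading does not mark.
- Report sensitivity with false positives per monitored hour, counting only hours that Corticare monitored and the formal readers read. If specificity is kept, fix its unit in advance.
- Keep investigator rejection as a separate measure of operational false alarms.
- State whether the formal readers are blinded to Corticare's alerts and to the real-time decisions. The documents do not establish that the formal reading is independent of them.
- Say in the SAP whether Aim 5A will still be reported after the monitoring changes.

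The cost is wording, since the formal reading is already planned. The small downside is that accuracy is known only after that reading, not in real time.
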